### 5.3.3 Use in nursing women

It is unknown whether nanrilkefusp alfa and pembrolizumab are excreted in human milk. Since many drugs are excreted in human milk, and because of the potential for serious adverse reactions in the nursing infant, patients who are breastfeeding are not eligible for enrollment.

Please also see section [5.1](#).

## 5.4 Screen failures

Screen failures are defined as patients who consent to participate in the clinical study but are not subsequently entered into the study. A minimal set of screen failure information is required to ensure transparent reporting of screen failure patients to meet the Consolidated Standards of Reporting Trials publishing requirements and to respond to queries from regulatory authorities. Minimal information includes demography, reason for screen failure, and AE/serious AE (SAE) as listed in section [8.3.2](#).

Patients may be rescreened once.

## 5.5 Criteria for temporarily delaying enrollment/administration of study intervention

See section [6.5](#).

## 6 STUDY INTERVENTIONS AND CONCOMITANT THERAPY

Study intervention is defined as any investigational intervention(s), marketed product(s), placebo, or medical device(s) intended to be administered to a study patient according to the study Protocol.

### 6.1 Study interventions administered

The interventions to be administered in this study are listed in [Table 6.1](#).

Patients will be treated with nanrilkefusp alfa 12 µg/kg subcutaneously on day 1 ( $\pm 1$  day for the cycle start), day 2, day 8, and day 9 in combination with pembrolizumab 200 mg IV on day 1 in 3-week cycles after all procedures and assessments have been completed.

Pembrolizumab will be administered as an IV infusion via peripheral or central venous line within 30 minutes after the first dose (day 1) of nanrilkefusp alfa in each 3-week cycle.

Sites should make every effort to target pembrolizumab infusion timing to be as close to 30 minutes as possible. However, given the variability of infusion pumps from site to site, a window between -5 minutes and +10 minutes is permitted (i.e., infusion time is 30 minutes [-5 min/+10 min]).

The Pharmacy Manual contains specific instructions for the preparation of the nanrilkefusp alfa dose and pembrolizumab infusion and administration of nanrilkefusp alfa and pembrolizumab.

**Table 6.1: Study interventions**

Intervention name	Dosage formulation	Unit dose strength(s)	Dosage level(s)	Route of administration	Regimen/treatment period	Sourcing
Product code: SOT101  International Nonproprietary Name: Nanrilkefusp alfa	Solution for injection	1.3 mg/vial	12 µg/kg	Subcutaneous	Administration on day 1 ( $\pm 1$ day for the cycle start), day 2, day 8, and day 9 of each 3-week cycle	Provided centrally by the sponsor
Pembrolizumab	Solution for infusion	100 mg/vial	200 mg	IV infusion via peripheral or central venous line	Administration within 30 minutes after the first dose of nanrilkefusp alfa (day 1) of each 3-week cycle	Provided centrally by the sponsor

### 6.2 Preparation, handling, storage, accountability

The investigator or designee must confirm appropriate temperature conditions have been maintained during transit for all study interventions received and any discrepancies are reported and resolved before use of the study interventions.

---

Only patients enrolled in the study may receive study interventions and only authorized site staff may supply or administer study interventions. All study interventions must be stored in a secure, environmentally controlled, and monitored (manual or automated) area in accordance with the labeled storage conditions with access limited to the investigator and authorized site staff.

The investigator, institution, or the head of the medical institution (where applicable) is responsible for study intervention accountability, reconciliation, and record maintenance (i.e., receipt, reconciliation, and final disposition records).

Further guidance and information for the final disposition of unused study interventions are provided in the Pharmacy Manual.

### **6.3 Measures to minimize bias: randomization and blinding**

This single-arm clinical trial will not be blinded.

### **6.4 Study intervention compliance**

Treatment for each patient will be recorded during the study.

### **6.5 Dose modification and toxicity management**

#### **6.5.1 Dose modification and toxicity management for nanrilkefusp alfa**

Dose modification and toxicity management for nanrilkefusp alfa for safety reasons will be discussed on a case-by-case basis between the site and the sponsor's medical monitor.

Transient pyrexia is a frequent AE after nanrilkefusp alfa injection. The use of, e.g., ibuprofen, and other non-steroid premedication can be considered according to local standard practice for prevention and treatment of fever.

Recommendations for clinical management of cytokine release syndrome are provided in section [6.5.3](#).

To minimize the risk for injection site reaction, subcutaneous injection sites should be rotated to different areas of the body (upper and lower extremities, each of the 4 quadrants of the abdomen).

To minimize the risks associated with shortening of the QT interval, vital signs and ECG must be closely monitored as per Protocol and institutional guidelines.

Liver function tests for nanrilkefusp alfa toxicity evaluation in this study will include AST, ALT, total bilirubin, and alkaline phosphatase.

Nanrilkefusp alfa-related hepatic toxicities should be managed as shown in [Table 6.2](#).

**Table 6.2: Management of nanrilkefusp alfa-related hepatic toxicities**

Nanrilkefusp alfa-related hepatic toxicity	Severity	Nanrilkefusp alfa dose modification
AST increased or ALT increased, or blood bilirubin increased	Grade 2 with AST or ALT $>3$ to $\leq 5 \times \text{ULN}$ or total bilirubin $>1.5$ to $\leq 3 \times \text{ULN}$	Withhold nanrilkefusp alfa Resume nanrilkefusp alfa if increased values return to grade $\leq 1$
	Grade $\geq 3$ with AST or ALT $>5 \times \text{ULN}$ or total bilirubin $>3 \times \text{ULN}$	Withhold nanrilkefusp alfa Resume nanrilkefusp alfa at 9 $\mu\text{g}/\text{kg}$ if increased values return to grade $\leq 1$ Permanently discontinue nanrilkefusp alfa on second occurrence of grade $\geq 3$ hepatic event

Please also refer to the IB, section [6.6](#) (Management guidelines for identified and potential risks).

## 6.5.2 Dose modification and toxicity management for pembrolizumab

### 6.5.2.1 Dose modification and toxicity management for immune-related AEs associated with pembrolizumab

AEs associated with pembrolizumab combination exposure, including coadministration with additional compounds, may represent an immune-related response. These immune-related AEs (irAEs) may occur shortly after the first dose or several months after the last dose of pembrolizumab combination treatment and may affect more than one body system simultaneously. Therefore, early recognition and initiation of treatment is critical to reduce complications. Based on existing clinical study data, most irAEs were reversible and could be managed with interruptions of pembrolizumab combination treatment, administration of corticosteroids, and/or other supportive care. For suspected irAEs, ensure adequate evaluation to confirm etiology or exclude other causes. Additional procedures or tests such as bronchoscopy, endoscopy, skin biopsy may be included as part of the evaluation. Dose modification and toxicity management guidelines for irAEs associated with pembrolizumab are provided in [Table 6.3](#).

#### 6.5.2.1.1 Attribution of toxicity

When study interventions are administered in combination, attribution of an AE to a single component is likely to be difficult. Therefore, while the investigator may attribute a toxicity event to the combination, to nanrilkefusp alfa alone, or to pembrolizumab alone, for AEs listed in [Table 6.3](#), both interventions must be held according to the criteria in [Table 6.3](#) and these cases should be discussed with the sponsor's medical monitor.

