### **Organ function**

Have adequate organ function as defined below. Specimens must be collected within 10 days prior to the start of study interventions.

9. Hematology:
  - 9.1. Absolute neutrophil count  $\geq 1500/\mu\text{L}$
  - 9.2. Platelets  $\geq 100\,000/\mu\text{L}$
  - 9.3. Hemoglobin  $\geq 9.0\text{ g/dL}$  (criteria must be met without packed red blood cell transfusion within the prior 2 weeks; patients can be on a stable dose of erythropoietin [ $\geq 3$  months])
10. Renal function: Creatinine clearance as measured by glomerular filtration rate  $\geq 30\text{ mL/min}$  using Cockcroft-Gault equation
11. Hepatic function: ALT/AST  $\leq 2.5 \times$  upper limit of normal (ULN) and total bilirubin  $\leq 1.5 \times \text{ULN}$  or direct bilirubin  $\leq \text{ULN}$  in patients without liver metastasis (benign hereditary hyperbilirubinemias, e.g., Gilbert's syndrome, are permitted if total bilirubin is  $\leq 3\text{ mg/dL}$ ). In patients with liver metastasis, ALT/AST  $\leq 5 \times \text{ULN}$  is allowed but total bilirubin must be  $\leq 2 \times \text{ULN}$ .
12. Prothrombin time and activated partial thromboplastin time  $\leq 1.5 \times \text{ULN}$

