**Table 6.3: Dose modification and toxicity management guidelines for irAEs associated with pembrolizumab**

General instructions:				
irAEs	Toxicity grade (CTCAE version 5.0)	Action with pembrolizumab	Corticosteroid and/or other therapies	Monitoring and follow-up
Pneumonitis	Grade 2	Withhold	Administer corticosteroids (initial dose of 1 to 2 mg/kg prednisone or equivalent) followed by taper	Monitor patients for signs and symptoms of pneumonitis
	Recurrent grade 2, grade 3, or grade 4	Permanently discontinue	Add prophylactic antibiotics for opportunistic infections	Evaluate patients with suspected pneumonitis with radiographic imaging and initiate corticosteroid treatment

irAEs	Toxicity grade (CTCAE version 5.0)	Action with pembrolizumab	Corticosteroid and/or other therapies	Monitoring and follow-up
Diarrhea/colitis	Grade 2 or grade 3	Withhold	Administer corticosteroids (initial dose of 1 to 2 mg/kg prednisone or equivalent) followed by taper	Monitor patients for signs and symptoms of enterocolitis (i.e., diarrhea, abdominal pain, blood, or mucus in stool with or without fever) and of bowel perforation (i.e., peritoneal signs and ileus)  Patients with grade $\geq 2$ diarrhea suspecting colitis should consider gastrointestinal consultation and performing endoscopy to rule out colitis  Patients with diarrhea/colitis should be advised to drink liberal quantities of clear fluids. If sufficient oral fluid intake is not feasible, fluid and electrolytes should be substituted via IV infusion
	Recurrent grade 3 or grade 4	Permanently discontinue		
AST or ALT elevation or increased bilirubin	Grade 2 a	Withhold	Administer corticosteroids (initial dose of 0.5 to 1 mg/kg prednisone or equivalent) followed by taper	Monitor with liver function tests (consider weekly or more frequently until liver enzyme value returned to baseline or is stable)
	Grade 3 b or grade 4 c	Permanently discontinue	Administer corticosteroids (initial dose of 1 to 2 mg/kg prednisone or equivalent) followed by taper	

irAEs	Toxicity grade (CTCAE version 5.0)	Action with pembrolizumab	Corticosteroid and/or other therapies	Monitoring and follow-up

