	Grade 3	Withhold or discontinue based on the event e		
	Recurrent grade 3 or grade 4	Permanently discontinue		

irAEs	Toxicity grade (CTCAE version 5.0)	Action with pembrolizumab	Corticosteroid and/or other therapies	Monitoring and follow-up

AE(s), adverse event(s); ALT, alanine transaminase; AST, aspartate transaminase; CTCAE, Common Terminology Criteria for Adverse Events; DRESS, drug rash with eosinophilia and systemic symptom; irAE(s), immune-related AE(s); IV, intravenous; SJS, Stevens-Johnson syndrome; T1DM, type 1 diabetes mellitus; TEN, toxic epidermal necrolysis; ULN, upper limit of normal
 
Note: Non-irAE will be managed as appropriate, following clinical practice recommendations.
 
a AST/ALT: >3.0 to 5.0×ULN if baseline normal; >3.0 to 5.0×baseline, if baseline abnormal; bilirubin:>1.5 to 3.0×ULN if baseline normal; >1.5 to 3.0×baseline if baseline abnormal
 
b AST/ALT: >5.0 to 20.0×ULN, if baseline normal; >5.0 to 20.0×baseline, if baseline abnormal; bilirubin:>3.0 to 10.0×ULN if baseline normal; >3.0 to 10.0×baseline if baseline abnormal
 
c AST/ALT: >20.0×ULN, if baseline normal; >20.0×baseline, if baseline abnormal; bilirubin: >10.0×ULN if baseline normal; >10.0×baseline if baseline abnormal
 
d The decision to withhold or permanently discontinue pembrolizumab is at the discretion of the investigator or treating physician. If control achieved or grade ≤2, pembrolizumab may be resumed.
 
e Events that require discontinuation include but are not limited to: encephalitis and other clinically important irAEs (e.g., vasculitis and sclerosing cholangitis)
				

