### 6.8.1 Rescue medication and supportive care

Patients should receive appropriate supportive care measures as deemed necessary by the treating investigator. Suggested supportive care measures for the management of AEs with potential immunologic etiology are outlined along with the dose modification guidelines in section [6.5](#).

Note: If after the evaluation of the event it is determined not to be related to pembrolizumab, the investigator does not need to follow the treatment guidance. Refer to section [6.5](#) for guidelines regarding dose modification and supportive care.

It may be necessary to perform conditional procedures such as bronchoscopy, endoscopy, or skin photography as part of evaluation of the event.

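### The protocol conflicts with itself on whether nanrilkefusp alfa may resume after a first grade ≥3 liver event attributed to it

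*Protocol*

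**What the plan says.** Five places in the protocol bear on a rise in AST, ALT or bilirubin.

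- **Table 6.2** (section 6.5.1) covers liver toxicity related to nanrilkefusp alfa. At grade ≥3 the drug is withheld and may resume at a reduced dose "if increased values return to grade" ≤1. The permanent stop comes later: "Permanently discontinue nanrilkefusp alfa on second occurrence of grade" ≥3.
- **Table 6.3** covers immune-related events associated with pembrolizumab. Its row "AST or ALT elevation or increased bilirubin" says withhold at grade 2 and permanently discontinue at grade 3 or 4, with no allowance for a first occurrence. The action column names pembrolizumab only.
- **Section 6.5.2.1.1** notes that attribution to one drug is difficult. For events listed in Table 6.3 it then says "both interventions must be held according to the criteria in" that table, including when the investigator blames nanrilkefusp alfa alone. These cases are also to be discussed with the medical monitor.
- **Section 6.5.2.1.3** requires all study interventions to end if the toxicity does not resolve or the resumption criteria are not met.
- **Section 7.1** lists, as a mandatory reason for stopping study interventions, any related toxicity for which section 6.5 specifies permanent discontinuation. Later it allows nanrilkefusp alfa to continue when pembrolizumab has to stop, except in the Czech Republic, where both stop.

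On grading, Table 6.2 sets its bands in multiples of ULN only. The Table 6.3 footnotes switch to multiples of the patient's own value when that is raised, for example up to "5.0×baseline, if baseline abnormal" for grade 2 AST/ALT. Inclusion criterion 11 reads "In patients with liver metastasis, ALT/AST" up to 5 × ULN is allowed, with total bilirubin up to 2 × ULN.

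**The concern.** The event at issue is serious and foreseeable, and the instructions for it are mandatory. If two sections give different answers on restarting nanrilkefusp alfa, sites will treat the same event differently, and a patient may be re-exposed at one site and stopped at another.

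The analysis is affected too. Section 8 of the protocol allows no waivers. Section 6.5.3 says that site changes to the cytokine release syndrome table are not deviations, but nothing similar covers the liver tables. So either handling could be called a deviation, depending on which table is taken to govern. That feeds the per-protocol population (SAP 9.6, which excludes major deviations), the tables of temporary and permanent discontinuation and dose reduction (SAP 12.8.1.1), and the compliance measure, which allows for dose reductions made per protocol (SAP 10.14).

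**Working it through.** No stated figure has to be reproduced. The check sets the rules side by side and then compares the two grading scales.

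**Step 1. One event under each rule.** Take a patient with normal baseline and a first ALT of 8 × ULN, attributed to nanrilkefusp alfa alone. Table 6.2 puts grade ≥3 above 5 × ULN. Table 6.3 puts grade 3 above 5 and up to 20 × ULN. Both call this event grade 3.

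| Source | Consequence for nanrilkefusp alfa |
|---|---|
| Table 6.2 | Withhold; may resume at a reduced dose on return to grade ≤1 |
| 6.5.2.1.1 with Table 6.3 | Hold by the criteria of a table whose entry for this grade is permanent discontinuation |
| 6.5.2.1.3 | Table 6.3 offers no route to resume at this grade, so all study interventions end |
| 7.1, mandatory list | Study interventions end if section 6.5 specifies permanent discontinuation; both tables sit in section 6.5 and the list does not say which one governs |
| 7.1, later sentence | May continue after pembrolizumab stops (not in the Czech Republic) |

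The first and last rows allow a restart. The second and third, read together, do not. The fourth does not decide the matter.

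**Step 2. Does scope separate the tables?** Table 6.2 is for nanrilkefusp alfa-related events and Table 6.3 for immune-related ones, and section 6.5.2.1.2 makes the joint hold depend on the event being considered immune-related. That would separate them if attribution decided which table to open. Section 6.5.2.1.1 removes that test, because it applies Table 6.3 to any event the table lists, and liver enzymes and bilirubin are listed.

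**Step 3. The Czech Republic.** Where Table 6.3 is applied and pembrolizumab is permanently stopped, section 7.1 stops nanrilkefusp alfa as well. The Table 6.2 restart is then unavailable for that event, and Table 6.2 does not say so.

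**Step 4. Grading when baseline is abnormal.** Take a patient with liver metastasis and a baseline ALT of 4 × ULN, which criterion 11 permits.

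- Table 6.3: grade 2 starts above 3 × 4 = 12 × ULN, and grade 3 above 5 × 4 = 20 × ULN.
- Table 6.2: grade 2 starts above 3 × ULN, and grade ≥3 above 5 × ULN.
- A drug-related rise to 10 × ULN is grade ≥3 in Table 6.2. It is 10 / 4 = 2.5 × baseline, which is below grade 2 in Table 6.3.

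Table 6.2 gives no multiple for grade ≤1. If its own ULN bands define it, ALT must fall to 3 × ULN or less, below this patient's starting value of 4. If the baseline rule of Table 6.3 is borrowed, anything up to 12 × ULN qualifies, and the rise to 10 × ULN meets the trigger and the resumption condition at once. Neither reading is stated.

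**Step 5. Who is affected by step 4.** The eligibility ceilings with liver metastasis overlap the Table 6.2 grade 2 bands for ALT/AST (>3 to 5 × ULN, the whole band) and for bilirubin (>1.5 to 2 × ULN). Without liver metastasis the ALT/AST ceiling is 2.5 × ULN, below the band.

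**The case against.** The best defence is that the two tables can be followed together. Section 6.5.2.1.1 says held, not discontinued, and Table 6.2 also withholds nanrilkefusp alfa at grade 2 and above, so the hold step agrees. The Table 6.3 action column names pembrolizumab only, and section 7.1 separates the drugs. A site could hold both, stop pembrolizumab under Table 6.3 and manage nanrilkefusp alfa under Table 6.2. Medical monitor discussion is available in sections 6.5.1 and 6.5.2.1.1, and Table 6.2 refers to the Investigator's Brochure, which is not among the documents and might settle the question.

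Much of this stands. A reader might infer that no site could ever satisfy both tables. The documents do not support that, because extending permanent discontinuation to nanrilkefusp alfa depends on reading Table 6.3 with sections 6.5.2.1.3 and 7.1. But those sections do point that way, so the harmonising reading is only one of two. Discussion with the monitor does not say which table governs.

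Two further inferences are tempting and should not be drawn.

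- Section 6.8.1 says that if "it is determined not to be related to pembrolizumab, the investigator does not need to follow the treatment guidance". A reader might take this as release from the hold and stop rules. The note sits under supportive care, and its next sentence sends dose modification back to section 6.5, so the natural reading is narrower.
- A reader might infer that patients entering at >3 to 5 × ULN are already at the withholding level, or can never resume. Table 6.2 covers drug-related increases only, so an entry value triggers nothing by itself. Resumption is out of reach on return to baseline only if grade ≤1 is read on fixed ULN multiples.

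The difference in grading scales is also not a contradiction by itself: at 10 × ULN in step 4, Table 6.2 acts and Table 6.3 does not, and a site can comply with both. The gap is the undefined resumption grade.

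**Conclusion.** The point holds in a narrow form. For a first grade ≥3 AST, ALT or bilirubin event attributed to nanrilkefusp alfa, the protocol supports two incompatible answers on whether that drug may resume, and nothing in it ranks them. Separately, Table 6.2 does not say how grade ≤1 is judged when baseline is abnormal, which matters for patients with liver metastasis admitted above 3 × ULN for ALT/AST or above 1.5 × ULN for bilirubin.

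The size cannot be put in numbers, because the documents give neither liver event counts nor baseline distributions. It should not be read as covering every grade ≥3 liver event, since Table 6.2 is limited to nanrilkefusp alfa-related toxicity. No effect on the response rate is claimed. Recruitment stopped after the August 2023 futility analysis (SAP 6.1), so future exposure is confined to patients still on treatment, including any under continued access (protocol 6.6). Past events still need consistent classification. The conclusion assumes that the Investigator's Brochure does not already resolve the conflict. Even if it does, the protocol should say so.

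**What to change.** Reconcile Table 6.2, Table 6.3 with its footnotes, and sections 6.5.2.1.1, 6.5.2.1.3 and 7.1, so that one rule governs each drug for each liver event, with the Czech provision carried through. State in Table 6.2 which grading basis applies, for the trigger and for resumption, when baseline is abnormal, and check it against inclusion criterion 11. Say in section 6.8.1 that the note concerns supportive-care guidance only, if that is the intent. Which clinical rule applies is for the sponsor's medical team, and no view is offered here.

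The cost is a protocol clarification or amendment. For events that have already occurred, the data review meeting before database lock (SAP 9.6) should record which rule was taken to govern, so that deviations and dose reductions are classified the same way throughout.

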#### 6.5.2.1.2 Holding study interventions

When study interventions are administered in combination, if the AE is considered immune-related, both interventions should be held according to recommended dose modifications.

#### 6.5.2.1.3 Restarting study interventions

Patients may not have any dose modifications (no change in dose or schedule) of pembrolizumab in this study, as described in [Table 6.3](#).

If the toxicity does not resolve or the criteria for resuming treatment are not met, the patient must be discontinued from all study interventions.

If the toxicities do resolve and conditions are aligned with what is defined in [Table 6.3](#), the combination of nanrilkefusp alfa and pembrolizumab may be restarted at the discretion of the investigator. In these cases where the toxicity is attributed to the combination or to nanrilkefusp alfa alone, re-initiation of pembrolizumab as a monotherapy may be considered after communication with and agreement by the sponsor.

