1. Criteria for discontinuation of study interventions are listed in section 7.1. In case nanrilkefusp alfa needs to be discontinued for reasons other than disease progression, pembrolizumab treatment can continue for up to a total of 35 administrations (approximately 2 years) in patients without disease progression or unacceptable toxicity. A schedule of activities for patients who continue pembrolizumab after discontinuation of nanrilkefusp alfa is shown in section 1.3.2. In case pembrolizumab needs to be discontinued, nanrilkefusp alfa treatment can continue until disease progression or unacceptable toxicity and the schedule of activities for patients receiving nanrilkefusp alfa combined with pembrolizumab will apply (not applicable in the Czech Republic). In the Czech Republic: In case pembrolizumab needs to be discontinued, nanrilkefusp alfa treatment will be discontinued as well.
2. No study-specific procedures are to be performed before ICF signature.
3. Age at screening and gender
4. Primary tumor location, histology/cytology, initial diagnosis date, lines of previous treatment, start and stop dates of the treatments before this study, any prior mutations/genetic analysis (e.g., EGFR, ALK mutations), and the date of the latest disease progression if not coinciding with the stop date
5. Before nanrilkefusp alfa administration
6. Every 30 ( $\pm 2$ ) days until 120 ( $\pm 2$ ) days after the last dose of pembrolizumab or 30 ( $\pm 2$ ) days after the last dose of nanrilkefusp alfa, whichever is later
7. Before nanrilkefusp alfa administration and afterwards as clinically required
8. Follow-up visits 30 ( $\pm 2$ ) days and 90 ( $\pm 2$ ) days after the last dose of nanrilkefusp alfa and/or pembrolizumab (whichever occurs later)
9. Before and after nanrilkefusp alfa administration as described in section 8.2.3
10. In case of proteinuria  $\geq 100$  mg/dL at screening, a 24-hour urine analysis will have to be performed (before the start of nanrilkefusp alfa treatment) to document 24-hour proteinuria levels and a urine test will continue during the treatment period. In case of increase of proteinuria with  $\geq 300$  mg/dL (at any time), a 24-hour urine analysis will be performed.
11. Using either echocardiography or MUGA; the method chosen needs to stay the same throughout the trial

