of symptoms following initial improvement; hospitalization indicated for other clinical sequelae (e.g., renal impairment, pulmonary infiltrates)  Grade 4: Life-threatening; pressor or ventilator support indicated	
 
○ Antihistamines
 
○ NSAIDs
 
○ Acetaminophen
 
○ Narcotics
 
○ Oxygen
 
○ Pressors
 
○ Corticosteroids
 
 
 
● Increase monitoring of vital signs as medically indicated until the patient is deemed medically stable in the opinion of the investigator.
 
● Hospitalization may be indicated.
 
 
**In cases of anaphylaxis, epinephrine should be used immediately.
 
Patient is permanently discontinued from further study drug treatment.
	

Appropriate resuscitation equipment should be available at the bedside and a physician readily available during the period of drug administration. For further information, please refer to CTCAE version 5.0 at <http://ctep.cancer.gov>.

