## 7 DISCONTINUATION OF STUDY INTERVENTION AND PATIENT DISCONTINUATION/WITHDRAWAL

### 7.1 Discontinuation of study intervention

Discontinuation of study interventions does not represent withdrawal from the study.

A patient must be discontinued from study interventions but continue to be monitored in the study (if possible) for any of the following reasons:

- Confirmed radiographic disease progression (please refer to section 10.2)
- Clinical disease progression (investigator's assessment)
- AE (intercurrent illness or study intervention-related toxicity that would, in the judgment of the investigator, affect assessments of the patient's clinical status to a significant degree or require discontinuation of study interventions)
- Patient may withdraw from the study at any time for any reason; the investigator must make every effort to determine the reason for this decision and record it in source documentation of the patient
- Discontinuation of treatment may be considered for patients who have attained a confirmed complete response (CR) and have been treated for at least 8 cycles (at least 24 weeks), receiving 2 cycles of the combination including 2 doses of pembrolizumab and at least 80% of the planned doses of nanrilkefusp alfa beyond the date when the initial CR was declared
- Any study intervention-related toxicity specified as a reason for permanent discontinuation as defined in the guidelines for dose modification due to AEs in section 6.5
- Death of the patient
- Pregnancy of the patient
- Concomitant treatment with a prohibited medication, including further lines of systemic anti-cancer therapy (also see section 6.8.2)
- Patient's non-compliance
- Lost to follow-up
- Study terminated by the sponsor

Pembrolizumab will be discontinued after the completion of 35 administrations (approximately 2 years; also see section 6.6).

In case nanrilkefusp alfa needs to be discontinued for reasons other than disease progression, pembrolizumab treatment can continue for up to a total of 35 administrations (approximately 2 years) in patients without disease progression or unacceptable toxicity. In case pembrolizumab needs to be discontinued, nanrilkefusp alfa treatment can continue until disease progression or unacceptable toxicity (not applicable in the Czech Republic). In the Czech Republic: In case pembrolizumab needs to be discontinued, nanrilkefusp alfa treatment will be discontinued as well.

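### Outside the Czech Republic, the protocol gives conflicting instructions on whether nanrilkefusp alfa may continue when an immune-related AE means pembrolizumab cannot be resumed

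*Protocol*

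**What the plan says.** Four places in the protocol bear on this.

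- **Section 6.5.2.1.3** (restarting after an immune-related AE): "If the toxicity does not resolve or the criteria for resuming treatment are not met, the patient must be discontinued from all study interventions". Where an event resolves and Table 6.3 allows it, the combination may restart. Pembrolizumab alone is possible with the sponsor's agreement when the event is attributed to the combination or to nanrilkefusp alfa. The section offers no route for nanrilkefusp alfa alone.
- **Section 7.1, list of mandatory reasons to stop study interventions.** One bullet reads "Any study intervention-related toxicity specified as a reason for permanent discontinuation" and refers to section 6.5.
- **Section 7.1, closing paragraph:** "In case pembrolizumab needs to be discontinued, nanrilkefusp alfa treatment can continue until disease progression or unacceptable toxicity". The exception is "In the Czech Republic: In case pembrolizumab needs to be discontinued, nanrilkefusp alfa treatment will be discontinued as well". Footnote 1 of section 1.3.1 gives the same permission and exception, and adds that the combination visit schedule still applies.
- **Table 6.4** (infusion reactions), grade 3 or 4: "Patient is permanently discontinued from further study drug treatment". The instruction for grade 2 reactions that occur despite premedication also speaks only of study drug.

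Section 6.5.2.1.1 adds that, for Table 6.3 events, "both interventions must be held according to the criteria in" that table, whatever the attribution, and that these cases should be discussed with the sponsor's medical monitor.

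**The concern.** A site with a patient who has had a serious immune-related event can find one section that stops both drugs and another that lets the immune-activating cytokine continue alone. Neither refers to the other on this point. What is at stake first is consistent management of patients with serious toxicity.

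There is a smaller statistical consequence. How much nanrilkefusp alfa is given without pembrolizumab, and which discontinuations are recorded for which drug, could depend on the section followed. That would affect how the exposure and per-drug discontinuation summaries are interpreted. The matter also remains relevant for anyone still on treatment or in continued access under section 6.6.

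**Working it through.** No arithmetic applies, and the plan states no figure on this point. The check is to follow each type of patient through the current text.

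| Situation | Section 6.5.2.1.3 | Closing paragraph of 7.1 and footnote 1 of 1.3.1 | Result |
|---|---|---|---|
| Immune-related event does not resolve | Both drugs stop | Nanrilkefusp alfa may continue, unless the event counts as unacceptable toxicity | Depends on an undefined term |
| Event has improved, but Table 6.3 permanently discontinues pembrolizumab | Resuming criteria not met, so both drugs stop | Nanrilkefusp alfa may continue alone | Opposite answers |
| Event resolves and Table 6.3 allows resumption | Combination may restart, or pembrolizumab alone with sponsor agreement | Not triggered | No conflict |
| Pembrolizumab ends after 35 administrations | Not triggered | Nanrilkefusp alfa may continue alone | No conflict |
| First two situations, in the Czech Republic | Both drugs stop | Both drugs stop | No conflict |
| Pembrolizumab infusion reaction | Does not apply (covered by 6.5.2.2) | Nanrilkefusp alfa may continue alone | Unclear, because Table 6.4 does not name the drug |

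**The second row is the core case.** Examples are grade 3 nephritis and grade 2 myocarditis, for both of which Table 6.3 permanently discontinues pembrolizumab. The row assumes that a permanent stop of pembrolizumab means the resuming criteria in 6.5.2.1.3 are not met. That is the natural reading, but the protocol does not spell it out. The action column of Table 6.3 covers pembrolizumab only, so the table itself does not say what happens to nanrilkefusp alfa. Section 6.5.2.1.1 requires both drugs to be held, but a hold does not settle permanent discontinuation.

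**Scope within Table 6.3.** Pneumonitis, diarrhea/colitis, nephritis, neurological toxicity, myocarditis, exfoliative skin conditions and the residual category all have a permanent-discontinuation row. Hypophysitis, hyperthyroidism and hypothyroidism at grade 3 or 4 leave a choice between withholding and stopping. Grade 2 hyperthyroidism and hypothyroidism let pembrolizumab continue, so no conflict arises there. Hepatic events are set aside because Table 6.2 has its own nanrilkefusp alfa instructions.

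**Precedence.** Neither the sections above nor the country-specific appendix (10.5) ranks the two rules. The appendix removes the permission for the Czech Republic only. The SAP counts a stop of either drug or both as discontinuation of combination treatment (12.8.1.1), which does not say which drugs must stop.

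**The case against.** The strongest case is that the texts can be read together. Section 7.1 is not uniformly permissive: its bullet referring to section 6.5 makes toxicities named there for permanent discontinuation a mandatory reason to stop. The closing paragraph is optional wording, whereas 6.5.2.1.3 is mandatory and more specific. The permission has a use unrelated to toxicity, namely the end of pembrolizumab after 35 administrations. An event that does not resolve could be classed as unacceptable toxicity, at which point the permission ends by its own terms. Section 6.5.2.1.1 directs Table 6.3 cases to the medical monitor, and 6.5.1 sends nanrilkefusp alfa dose changes for safety to case-by-case discussion with the same role.

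Much of this stands as a reasonable interpretation, but the protocol states none of it. With the bullet included, 7.1 contains both rules. The permission is not limited by reason for stopping, and unacceptable toxicity is not defined. Discussion with the monitor may reduce divergence but supplies no rule. The Czech regulator's comment in the amendment summary took the single-agent option to concern toxicity stops. That is background only and does not decide the reading.

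A reader might also infer more than the documents support:

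- **That sites do act differently.** The documents show only that they could.
- **That 6.5.2.1.3 also governs infusion reactions.** It sits under the immune-related AE section. For infusion reactions the problem is the wording of Table 6.4 against 7.1.
- **That a number of patients can be given.** An assumed 5–10% rate of pembrolizumab discontinuation for toxicity, applied to the planned 320, gives 0.05 × 320 = 16 to 0.10 × 320 = 32. The rate is not in the documents, and the product would include Czech patients and hepatic cases. SAP section 6.1 also records that recruitment stopped after the August 2023 futility analysis.
- **That the response and progression endpoints are counted differently by site.** The SAP rules are the same everywhere. Best overall response runs from first dose to progression, death or new anti-cancer therapy, whichever drug continues (10.13.3). Exposure is derived for each drug (10.14).

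**Conclusion.** The conflict is real and is in current protocol text. It applies outside the Czech Republic to patients whose pembrolizumab cannot be resumed because of an immune-related AE. It is firmest where the event has improved but Table 6.3 bars pembrolizumab permanently, and weaker where the event persists and might be called unacceptable toxicity. The unclear drug reference in Table 6.4 is a separate, smaller defect.

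The conclusion rests on two points: that a permanent stop of pembrolizumab fails the resuming criteria of 6.5.2.1.3, and that no other text sets precedence. It does not depend on any rate or count. No sample size, futility boundary or other planned figure changes. The point is worth correcting because it concerns safety and costs little, not because it threatens the primary analysis. Which rule is right is not judged here.

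**What to change.** Reconcile section 6.5.2.1.3, section 7.1 (both the bullet referring to section 6.5 and the closing paragraph) and footnote 1 of section 1.3.1. They should give one answer on whether nanrilkefusp alfa may be given after pembrolizumab is stopped for an immune-related AE, and should cross-refer to each other. In Table 6.4, replace the reference to study drug with the named drug or drugs, for both the grade 2 and the grade 3 or 4 instructions, and align it with 7.1. The sponsor decides which rule applies.

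Optionally, if single-agent nanrilkefusp alfa remains possible, the SAP could flag responses first documented after the last pembrolizumab dose.

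The cost is wording in four places in the next amendment. The optional flag is one derived variable from dosing and assessment dates already collected. No new data are needed.
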